**STUDY PROTOCOL AND STATISTICAL ANALYSIS PLAN**

## 1. Methods

### 1.1. Study design

This will be a multisite randomized active-comparator controlled clinical trial. Due to the nature of the intervention, subjects and investigators will not be able to be masked to the intervention. The assessor will not be able to be masked to group assignments, as the presence or absence of certain variables in the dataset, namely the perturbation level, will immediately reveal group assignment.

**Sample Size Estimation and Study Timeline:** Using the pilot data, a Cohen's d effect size of 0.39 was calculated and a two-tailed power analysis ( $\alpha=0.05$ ) was conducted. For the observed effect size, an estimated sample size of 214 participants would achieve 80% power. Using this estimate, and the estimates of the participating sites of the number of potential subjects that could be recruited, enrollment is expected to last 12-18 months (Table 1).

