BWSS (Aretech LLC, Ashburn, VA) and the Training Responses in Postural Rehabilitation (TRiP) balance perturbation module (Aretech LLC, Ashburn, VA) will be the primary pieces of equipment required to complete this study. All study locations already have the ZeroG BWSS and TRiP module installed.

In addition to the equipment, several outcome measurements will be collected throughout the study duration. Balance specific measurements that will be collected include the BBS, an objective balance measure, and the Activities Specific Balance (ABC) scale, a subjective patient reported measure. When appropriate for the patient, an admission BBS is collected within 72 hours of admission at all study locations by the patient's primary therapist. This admission evaluation will be used to initially identify potential subjects with an admitting BBS of 21 or greater; this will be used as the pre-intervention assessment (pre-assessment) during data analysis. When patients are discharged, a follow-up BBS is typically collected at all study locations. However, discharge may not always occur in a timely fashion after the conclusion of the study. To address this, a post-intervention assessment (post-assessment) will be collected within 48 hours of the last study session if not already collected by the participant's primary therapist during that time. The patient reported ABC scale will be collected during the informed consent process and immediately following the last study session.

To evaluate gait, the objective self selected 10 Meter Walk Test (10MWT) assessment will be conducted. If not already conducted during the participant's admission evaluation, a 10MWT pre-assessment will be conducted by site investigators within 48 hours prior to the first study session. A post-assessment 10MWT will be collected within 48 hours of the last study session if not already collected by the participant's primary therapist during that time.

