**Table 2. Schedule of Study Procedures and Assessments**

Procedure	Admission	Screening	Pre- Intervention	Treatment Sessions						Post- Intervention
				1	2	3	4	5	6	
BBS	X									X
Report generation	X									
Informed consent		X								
Participant group assignment			X							
Collection of demographic and other secondary information as described below 				X						X
Additional stroke information 				X						X
ABC scale				X						X
10MWT				X						X
BWSS Control Intervention					X	X	X	X	X	X
BWSS-P Intervention					X	X	X	X	X	X
TRiP/Perturbation level recording					X	X	X	X	X	X
System on-time/off-time recording					X	X	X	X	X	X
Data transfer										X

The described information can be collected, as available, any time after the subject has consented to the study, but before de-identified data is transferred to the Lead Site.

**Subject assignment:** Consented subjects will be assigned to either the BWSS Standard Intervention (Control) Group or BWSS with Balance Perturbations (BWSS-P) Intervention Group according to a pre-generated randomized assignment sheet. Each randomized assignment sheet will consist of equal BWSS Control and equal BWSS-P assignments whose order has been randomized using the random list generator at <https://www.random.org/lists/>. Co-Investigators at each site, who will not be delivering the study interventions directly, will be given a unique list with a number of assignments that is in proportion to the number of subjects expected to be recruited at the site; additional assignment lists will be generated if needed. These co-Investigators will be responsible for communicating group assignments to study therapists delivering the intervention, and for ensuring that randomization and treatment order is maintained. It is expected that if the assignment scheme is not maintained for whatever reason, that they will report the incident to the steering committee, described below, and how it was/or still needs to be rectified. No matter group assignment, all consented subjects will be asked to conduct all pre- and post-assessments.

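### Where no admission 10MWT exists, the plan lets unmasked site staff measure the baseline 10MWT after the arm is known

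*Combined protocol and SAP*

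**What the plan says.** **Masking.** The study design section states that "subjects and investigators will not be able to be masked to the intervention", and of outcome assessment, "The assessor will not be able to be masked to group assignments". The reason given for the second is that the perturbation level in the dataset reveals the group.

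**Baseline 10MWT.** The Equipment and Instruments section sets a condition, "If not already conducted during the participant's admission evaluation", and then says "a 10MWT pre-assessment will be conducted by site investigators within 48 hours prior to the first study session". The recruitment and pre-assessment paragraph repeats the rule.

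**Other baselines.** The BBS baseline is the admission score. The ABC is placed during the consent process in one paragraph and directly after consent in another.

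**Assignment.** The Subject assignment paragraph says "Consented subjects will be assigned to either the BWSS Standard Intervention (Control) Group" or to the perturbation group, with no other precondition. The list is held locally: "Co-Investigators at each site, who will not be delivering the study interventions directly, will be given a unique list". These co-investigators pass assignments to the treating therapists. The paragraph ends: "No matter group assignment, all consented subjects will be asked to conduct all pre- and post-assessments". In Table 2 the row "Participant group assignment" stands below consent and above the ABC and 10MWT rows.

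**Analysis.** The Data Analysis section names the 10MWT among five primary outcome measures. It compares pre and post values by 2-way ANOVA or a mixed-effects analysis, and also names ANCOVA without listing the covariates.

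**The concern.** A baseline is useful in a randomized comparison because the arm cannot have influenced it. If the walk is timed after the arm is known, that protection is lost. The 10MWT is called objective, but it is done at a self-selected pace. The wording of the instruction, encouragement from the tester, or the participant's own knowledge of the arm could change it.

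A shift in one arm's baseline moves that arm's mean change by the same amount in the opposite direction. If the baseline is an ANCOVA covariate, the shift enters multiplied by the regression slope, so adjustment carries part of the error into the estimate. The direction cannot be predicted from the documents.

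The exposure is also avoidable. The plan's reason for an unmasked assessor is that perturbation data identify the group, and before the first session no such data exist. Masking may be hard after treatment, but measuring the baseline before assignment is not.

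**Working it through.** **Is the order fixed anywhere?** Taking the provisions together:

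1. Assignment may happen at any time after consent.
2. The study-run 10MWT may happen at any time in the two days before session 1.
3. Assignment must reach the therapist before session 1, so the two windows can overlap.
4. The testers are site investigators, and the plan declares investigators unmasked. The co-investigators holding the list are kept from delivering treatment but not from assessing.
5. No sentence requires the walk to be recorded before the assignment is released, or requires a tester who does not know it.
6. The recruitment paragraph says procedures follow Table 2, whose row order puts assignment first. The column marks look shifted in the text available (intervention marks fall under sessions 2 to 6 and the post-intervention column). I therefore give the table little weight; the absence of an ordering rule is the stronger ground.

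**Which baselines are exposed?** Only the 10MWT of participants without an admission 10MWT. The BBS and any 10MWT from admission normally precede consent, and so assignment.

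**The plan's own figure.** For d = 0.39, two-sided α = 0.05 and 80% power, the normal formula gives 2 × (1.960 + 0.842)² / 0.39² = 103.2, so 104 per arm and 208 in total. The t-test gives 105 per arm, 210 in total. The stated 214 is within 3% of both, and an unrounded d of 0.385 gives exactly 214 by the t-test. The figure is sound and does not bear on this point. I use it only for 214 / 2 = 107 per arm.

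**Illustration of size.** Two inputs are assumptions, because the documents give neither:

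- f, the share of participants with a study-run baseline 10MWT taken with the arm known;
- b, the arm-related shift in those baselines, in SDs of the change score.

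The net bias in the between-arm difference in change is δ = f × b. The standard error is √(2/107) = 0.1367 SD. With no true effect, the two-sided rejection rate is 1 − Φ(1.96 − δ/0.1367) + Φ(−1.96 − δ/0.1367).

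Example: f = 0.50 and b = 0.1 give δ = 0.05 and δ/0.1367 = 0.366. The rate is 1 − Φ(1.594) + Φ(−2.326) = 0.055 + 0.010 = 0.065.

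| Share f | b = 0.1 SD | b = 0.2 SD |
|---|---|---|
| 10% | 5.1% | 5.2% |
| 25% | 5.4% | 6.5% |
| 50% | 6.5% | 11.3% |
| 100% | 11.3% | 31% |

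In ANCOVA the shift in the estimate would be the slope times δ. With an assumed slope of 0.7 and δ = 0.10, that is 0.7 × 0.10 = 0.07 SD of change.

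**The case against.** The strongest reply is that the study-run 10MWT is a fallback. If most participants are walked at admission, few baselines are exposed, and at a 10% share the table shows almost no effect. That stands, and it limits the point.

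It can also be said that the paragraph on pre-assessments comes before the one on assignment, so sites may well measure first. That is possible, but paragraph order is not a rule, and Table 2's row order points the other way.

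No passage says the tester has been told the arm. That also stands: the documents support that the tester can know, not that the tester does.

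A reader might infer more than the text allows in four ways:

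- **That the closing sentence of Subject assignment puts the pre-assessments after assignment.** It says only that both arms do every assessment.
- **That all baselines are compromised.** The admission BBS is not in the usual case. The ABC hardly is, although neither paragraph expressly puts it before disclosure.
- **That the false-positive rate is 11%.** With a 0.1 SD shift, this requires every participant to have an exposed baseline.
- **That the bias can be read as a fraction of d = 0.39.** The plan does not say which outcome that effect size came from, so it cannot be applied to the 10MWT.

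**Conclusion.** The point holds for one measurement. Followed as written, the plan permits the baseline of a primary outcome to be taken by unmasked staff after assignment, for participants with no admission 10MWT. Bias is possible, not shown. Its size runs from negligible to material: with 107 per arm and an assumed shift of 0.1 SD of change, the false-positive rate lies between 5.1% (10% share) and 11.3% (100% share). These figures rest on an assumed share, an assumed shift in one direction and an analysis of change scores; none of these figures is a finding about the trial. The sample size is unaffected. The gap is worth closing because doing so costs almost nothing and an arm-aware baseline cannot be remeasured once treatment has begun.

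**What to change.** In the Subject assignment paragraph, state that the co-investigator releases the assignment only after the baseline 10MWT and the ABC have been completed and recorded. Place the assignment row of Table 2 below those rows. The ABC is included only to settle the slight ambiguity between the two paragraphs that time it. This costs one sentence and a reordered table, with no added visits, staff or participants.

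The Data Analysis section is written in the past tense, so data may already have been collected and a rule on order would come too late. In that case:

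- report, by arm, the dates (and times if held) of assignment and of the baseline 10MWT, and the number of baselines taken after assignment;
- run a sensitivity analysis of the 10MWT that excludes those baselines. It is supportive only, since the exclusion rests on timing that may itself differ by arm.

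This costs one extra table and one extra model, provided the dates were kept. Neither step addresses the unmasked post-treatment assessment, which is a separate matter.

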**Table 1. General Timeline**

Year 1	Month											
	1	2	3	4	5	6	7	8	9	10	11	12
Clinical Trial Registration 	X											
Purchasing 	X											
Staff Training/Check-in	X			X					X			
Steering Committee meeting	X	X	X	X	X	X	X	X		X	X	X
Enrollment Target 		12	12	12	12	12	12	12	12	12	12	12
Completion Target 			12	12	12	12	12	12	12	12	12	12
Interim data analysis (25% and 50% recruitment)							X				X	
Year 2	Month											
	13	14	15	16	17	18	19	20	21	22	23	24
Staff Training/Check-in	X											
Steering Committee meeting	X	X	X	X	X	X	X	X	X	X	X	X
Enrollment Target 	12	12	12	12	12	12	12					
Completion Target 	12	12	12	12	12	12	12	12				
Data analysis									X	X		
Manuscript preparation; Poster abstract submission										X	X	X
Clinical Trial Registration: Data updates 										X	X	

This study will be registered and maintained at clinicaltrials.gov; Registration will be completed prior to recruiting the first subject.

If grant funding is able to be attained, purchasing outlined in the grant will be completed in month 1 of the award period.

Enrollment and completion targets are estimates based on an 18 month enrollment period. For a 12 month enrollment period, the enrollment and completion targets would be 18 participants per month, with the completion target ending in month 13.

**Participants, Settings, and Inclusion/Exclusion Criteria:** To participate in this study, participants must be recruited at one of the three participating rehabilitation centers: Gaylord Specialty Healthcare (Wallingford, CT), MedStar National Rehabilitation Hospital (Washington, DC), or Spaulding Rehabilitation Hospital Cape Cod (Sandwich, MA).

To be eligible for study participation, subjects must meet the following *Inclusion Criteria*:

- Admitted to one of the listed study locations for inpatient rehabilitation following either

ischemic or hemorrhagic stroke and medically stable for the therapy program.

- Be 18 years of age or older.
- Discharge date of 10 days or longer at study consent
- Have at least a moderate fall risk or better, shown by an admission BBS score of 21/56 or greater.
  - Patients that score below 21 or are non-ambulatory will not be considered for this study.

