**Subject identification, recruitment, and pre-assessments:** As described above, qualifying patients will initially be screened/identified through internal reports generated at each study site summarizing admission BBS scores for recently admitted patients. Screening will continue until the target number of participants have completed the study and/or the pre-determined statistical guidelines have been met. After initial screening, the additional inclusion/exclusion criteria will be considered with attending physician approval and the patient approached for consent. After collecting informed consent, participants will be asked to complete an ABC scale pre-assessment. If it was not already conducted by the participant's primary physical therapist at admission, a 10MWT pre-assessment will be conducted within the 48 hours prior to the first treatment session. The admission BBS score will be counted as the participants' BBS pre-assessment. Study procedures and assessments will be conducted according to the general timeline shown in **Table 2**.

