**BWSS Standard Intervention Control Group:** The BWSS control group will conduct at least 2 and up to 6 study related therapy sessions. Study related therapy sessions will last a minimum of 15 minutes up to 30 minutes. Study sessions will be completed over a 2 to 3 week period as part of the subject's inpatient therapy program. Each session must have an active time of at least 15 minutes in the system to be included, up to 30 minutes for each session. To be as pragmatic and clinically relevant as possible, treatment sessions will be incorporated directly into the participants' normal care. Furthermore, we are allowing participants to complete 2 to 6 sessions as dictated by short or unexpected changes to the discharge planning timeline. During each session, participants will conduct balance exercises, including: marching, side-stepping, retro-ambulation, step-taps, and step-ups. They will also conduct various standard gait exercises, including: ambulation over the ground, going up and down stairs, and performing sit-to-stand transitions. Each of the 2 to 6 study sessions will be part of the subject's normal course of therapy. As this is an active clinical comparison, clinical parameters and progression, other than those described

above, will be determined by the treating therapist (i.e. percent body weight support and use of assistive devices) to ensure success and appropriate challenge to the subject.

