**BWSS-P Intervention Group:** The BWSS-P intervention group will also conduct 2 to 6 study sessions over a two-week period. Each session must have an active time of at least 15 minutes in the system, up to 30 minutes for each session. Participants in the BWSS-P group will conduct the same balance and gait exercises as the control group, however, these sessions will include eight perturbations, two in each direction (lateral left, lateral right, anterior, and posterior). Perturbations will occur while static/standing (lateral, anterior, posterior) and dynamically while ambulating (anterior, posterior). Each of the 2 to 6 study sessions will be part of the subject's normal course of therapy. As this is an active clinical comparison, clinical parameters and progression, other than those described above, will be determined by the treating therapist (i.e. percent body weight support and use of assistive devices) to ensure success and appropriate challenge to the subject. The TRiP or perturbation level will be progressed to the point of loss of balance, or very near loss, without recovery. The perturbation level should then be then decreased by one level for treatment. All 8 perturbations will occur at this level until it is clinically appropriate to progress again. The intensity of TRiP perturbation ranges from level 1 to 10, minimal to maximum, respectively.

**Post-Assessments:** After the completion of the subjects' final BWSS session before discharge, investigators will conduct an ABC and 10MWT post-assessment no longer than 48 hours following the final session. Follow-up BBS are often completed prior to discharge as part of patient/participant's standard of care. However, in the case that there is an unexpected delay or there is a significant length of time until the participant's discharge, a post-assessment BBS will be conducted no longer than 48 hours following the last session.

**Data Analysis:** Data were analyzed using GraphPad Prism (version 10; GraphPad Software, Boston, MA) and RStudio (version 4.2.2, Posit Software, PBC, Boston, MA] using the *car* package.

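### The session window is 2 to 3 weeks for control but two weeks for BWSS-P, so controls may have up to about 7 more days of recovery before outcome assessment

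*Combined protocol and SAP*

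**What the plan says.** All references are to section 1.1 of the combined protocol and SAP.

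- **Control arm** (BWSS Standard Intervention Control Group): "The BWSS control group will conduct at least 2 and up to 6 study related therapy sessions". On timing: "Study sessions will be completed over a 2 to 3 week period as part of the subject's inpatient therapy program".
- **Perturbation arm** (BWSS-P Intervention Group): "The BWSS-P intervention group will also conduct 2 to 6 study sessions over a two-week period".
- **Outcome timing.** Under Post-Assessments, "investigators will conduct an ABC and 10MWT post-assessment no longer than 48 hours following the final session". Under Equipment and Instruments, the BBS post-assessment "will be collected within 48 hours of the last study session if not already collected by the participant's primary therapist during that time".
- **Baseline** (Subject identification, recruitment, and pre-assessments): "The admission BBS score will be counted as the participants' BBS pre-assessment". The ABC baseline is taken at consent. The 10MWT baseline is taken at admission or in the 48 hours before the first session.
- **Length of stay.** The inclusion criterion is "Discharge date of 10 days or longer at study consent". The control-group paragraph adds that "we are allowing participants to complete 2 to 6 sessions as dictated by short or unexpected changes to the discharge planning timeline".

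Table 2 gives both arms one schedule, numbered by session and not by day. The Data Analysis section names no ANCOVA covariates and describes no summary of elapsed time by arm.

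**The concern.** The two arms are meant to differ only in the eight perturbations per session. Exercises, number of sessions, minutes per session and therapist discretion are the same. A calendar window that differs by arm adds a second difference.

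The window matters because outcomes are not measured at a fixed day after randomisation. They follow the last session, so a longer session window allows a longer interval from baseline to outcome. The additional days bring recovery and ordinary inpatient therapy, not more study sessions, which are capped at six in both arms. Balance and gait scores of stroke rehabilitation inpatients may rise with time and usual care. If some controls use the third week, part of the between-arm difference would reflect interval length.

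Randomisation does not protect against this, because the rule applies after assignment and depends on it. Masking does not protect either: the treating therapists know the assignment. The planned analysis by number of sessions would not reveal the problem, since six sessions in 14 days and six in 21 days look the same there.

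**Working it through.** **1. Permitted difference in time**

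| | Control | BWSS-P |
|---|---|---|
| Sessions | 2 to 6 | 2 to 6 |
| Minutes per session | 15 to 30 | 15 to 30 |
| Longest session window | 3 weeks = 21 days | 2 weeks = 14 days |
| Post-assessment limit after last session | 48 hours = 2 days | 48 hours = 2 days |
| Longest time from start of window to post-assessment | 21 + 2 = 23 days | 14 + 2 = 16 days |

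The difference is 23 − 16 = 7 days. The time from admission to the first session is added to the BBS interval in both arms and should balance by randomisation. The 7 days come from the window alone.

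**2. The plan's own sample size**

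Inputs from the sample size paragraph: d = 0.39, two-sided α = 0.05, power 80%, stated N = 214. Allocation is 1:1, so there are 107 per arm.

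- Normal approximation: n per arm = 2(1.960 + 0.842)² / 0.39², rounded up to 104, total 208.
- Two-sample t-test: 104.2, rounded up to 105 per arm, total 210.
- Power with 107 per arm: 0.81 by either method.

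The stated 214 is therefore reproduced to within 3%.

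**3. Illustration of what a shift would do**

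The documents give no recovery rate and no forecast of how many controls would use the third week. Both are assumed here:

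- G = recovery in SD units over two weeks, taken as linear and continuing into the third week, so one week gives 0.5 × G.
- f = share of controls who use the full third week.
- Shift towards control = 0.5 × G × f. Expected difference = 0.39 − shift, if G is on the same SD scale as the planned d.

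Power is for a two-sample t-test, two-sided α = 0.05, 107 per arm.

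| f | G | Shift (SD) | Expected d | Power | n per arm for 80% |
|---|---|---|---|---|---|
| 0 | any | 0 | 0.39 | 81% | 105 |
| 0.10 | 0.2 | 0.01 | 0.38 | 79% | – |
| 0.10 | 0.8 | 0.04 | 0.35 | 72% | – |
| 0.25 | 0.4 | 0.05 | 0.34 | 70% | 137 |
| 0.25 | 0.8 | 0.10 | 0.29 | 56% | 188 |
| 0.50 | 0.8 | 0.20 | 0.19 | 28% | 436 |

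The last row is an upper end: it needs half of all controls to use the whole third week and rapid recovery throughout.

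If perturbations had no effect at all, a shift of 0.05 or 0.10 SD would raise the two-sided rejection rate from 5% to 6.5% or 11.3%, with the excess in favour of control.

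**The case against.** The strongest reply is that this is a drafting slip. The BWSS-P paragraph says that arm will also have 2 to 6 sessions, the two paragraphs are otherwise parallel, and Table 2 shows one schedule. Nothing suggests a deliberate arm-specific window. That may well be right. But Table 2 counts sessions and not days, so it does not settle which window applies, and three sites schedule from this text. A slip in an operating rule still needs correcting.

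Second, discharge planning probably drives the real timing. The entry criterion of 10 days is shorter than either window, so many participants in both arms may leave before the windows differ. This stands as a reason to expect a small realised difference. It does not exclude one, because 10 days is a minimum.

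Third, the direction is not proven. Spreading the same sessions over three weeks also makes them less intensive, which could work against controls. Extra recovery and usual care seem the stronger influence, but that is a judgement.

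Fourth, G and f are assumed, and the plan does not name the outcome or the SD behind d = 0.39. This is correct: the table shows sensitivity and is not evidence of bias.

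Fifth, dates may be among data items not listed in the available text. The claim is therefore limited to this: no report of interval by arm is described.

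Sixth, the Data Analysis section is in the past tense, so enrolment may be over. If so, only the reporting part of the remedy remains useful.

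**Conclusion.** The concern holds. The plan as written sets a different session window for each arm and permits about 7 more days between baseline and outcome in controls only. That much follows from the text and needs no assumption.

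Whether this biased the comparison, and by how much, cannot be determined from the documents. It depends on how many controls used the third week and how fast such patients improve. If few did, the loss of power is slight (81% to between 79% and 72% at f = 0.10). At f = 0.25 it is material (70% to 56% for G from 0.4 to 0.8). The likelier direction is against BWSS-P, so the main risk is a missed or understated benefit, not a false claim of one.

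This should be fixed. Confidence is medium: the mismatch is certain, its consequence is not.

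**What to change.** - **Protocol.** State one identical session window and one identical post-assessment rule in both intervention paragraphs. Either window will serve; the investigators should choose.
- **Data.** Record the dates of the admission BBS, the first and last sessions, and each pre- and post-assessment.
- **SAP.** Report days from baseline to post-assessment by arm (mean, median, range) for BBS, ABC and 10MWT.
- **If participants were already treated under the unequal wording.** Give the same table and discuss any difference as a limitation.
- **What to avoid.** Do not restrict the analysis to participants within a common window. That selects on a post-randomisation variable and would remove only controls.

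The cost is one sentence in the protocol, a few date fields and one descriptive table. Table 2 lists no assessment dates, so they may have to be added or taken from the clinical record. Choosing the narrower window gives up a little scheduling freedom. The sample size does not change.

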Descriptive data is reported as mean (95% confidence interval). If hypothesis testing was done, data were reported with a p-value, and significance was set at  $\alpha=.05$ . The primary outcome measures used in our analyses were the BBS, ABC, 10MWT, CMS GG0130 Mobility scores, and CMS GG0170 Self-care scores. Data were determined to be missing completely at random and were dealt with via complete case analysis and mixed-effects analysis as applicable. Data were also assessed for violations in assumptions of their given tests, and were dealt with via non-parametric analysis as necessary.

Categorical data was analyzed using Chi-square testing. Unpaired t-tests or Mann-Whitney U tests were utilized as necessary to evaluate between-group differences in continuous outcome variables.

Analysis of covariance (ANCOVA) was used to account for between group differences while controlling for covariates. To evaluate if there were differences between pre- and post-intervention data, a 2-way analysis of variance (ANOVA) was utilized, with mixed-effects analysis being utilized when data was missing. Differences in average improvement by number of sessions completed were evaluated using a 2-way ANOVA. Differences in outcome measure between testing sites were analyzed using one-way ANOVA or Kruskal-Wallis testing. Multiple comparisons were analyzed using, Fisher's, Dunn's, Tukey's multiple comparison tests as appropriate.

References:

2. Parametric ANCOVA and the Rank Transform ANCOVA When the Data are Conditionally Non-Normal and Heteroscedastic - Stephen F. Olejnik, James Algina, 1984 [Internet]. [cited 2024 Apr 4]. Available from: <https://journals.sagepub.com/doi/10.3102/10769986009002129>

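### The Data Analysis section reads as a report of completed work, so the document does not show that its five primary outcomes and its choice of tests were fixed before the data were seen

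*Combined protocol and SAP*

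**What the plan says.** The design text of section 1.1 looks forward: "This will be a multisite randomized active-comparator controlled clinical trial". It plans to measure BBS, ABC and 10MWT before and after the intervention, and it fixes the admission BBS as the baseline value. Its one inferential statement is the sample size: a pilot d of 0.39, two-tailed .05, 80% power and 214 participants. The outcome behind that d is not named.

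The Data Analysis paragraph, in the same section, changes to the past tense:

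- Software: "Data were analyzed using GraphPad Prism".
- Outcomes: "The primary outcome measures used in our analyses were the BBS, ABC, 10MWT, CMS GG0130 Mobility scores, and CMS GG0170 Self-care scores".
- Missing data: "Data were determined to be missing completely at random and were dealt with via complete case analysis and mixed-effects analysis as applicable".
- Assumptions: "Data were also assessed for violations in assumptions of their given tests, and were dealt with via non-parametric analysis as necessary".

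It lists unpaired t-tests or Mann-Whitney tests for group differences, ANCOVA with unnamed covariates (two of its three references concern rank-transform ANCOVA), and two-way ANOVA or mixed-effects analysis. None is designated as the primary analysis. Significance is set at .05.

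**The concern.** A test at .05 carries a 5% false-positive rate only if the outcome and the test were fixed without knowledge of the results. An analysis plan exists to show that they were, and this document cannot serve that purpose. Its only list of primary outcomes and its only list of tests sit in a paragraph that describes analysis already done.

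There was also opportunity for results to influence choices. Investigators and assessor are unmasked, and Table 1 schedules interim data analyses at 25% and 50% of recruitment. The Data Analysis paragraph is not dated relative to those looks or to the final data.

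At stake is which results, if any, the trial may present as a confirmatory answer. The question is separate from whether each listed method is suitable. A multiplicity rule or a better model written now would not settle it.

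**Working it through.** **1. Prospective text against the Data Analysis paragraph.**

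| Item | Prospective text | Data Analysis paragraph |
|---|---|---|
| BBS, ABC, 10MWT | Scheduled; none called primary | Primary |
| GG0130, GG0170 | Not named | Primary |
| Decisive between-group test | None | Several alternatives, none decisive |
| Covariates | None | Mentioned, not named |
| Missing-data rule | None | Mechanism reported as a finding |
| Significance level | Two-tailed .05, for the power calculation | .05 per test |

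Tense alone could be a drafting habit, so the content matters more. Taken as written, a finding about why data are missing, and a statement that assumptions were assessed, require collected data.

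**2. The plan's own figure.** Inputs: d = 0.39, two-sided .05, 80% power, equal allocation.

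n per arm = 2(1.960 + 0.842)² / 0.39² = 2 × 7.849 / 0.1521 = 103.2, so 104 per arm and 208 in total.

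The t-test version gives 104.2, so 105 per arm and 210 in total. An unrounded d of 0.385 gives 106.9, so 107 per arm and exactly 214. The stated 214 is therefore reproduced within rounding of d. At 107 per arm and d = 0.39, power is 81.0% (t) to 81.4% (normal). The arithmetic is sound; what it lacks is a named outcome.

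**3. What freedom in the test could cost.** The setting is one outcome with no true effect and 214 / 2 = 107 per arm. Two things are assumed because the documents do not give them: normal data, and a baseline-to-post correlation of 0.5, 0.7 or 0.8. The six candidate tests are the t-test on the post score and on the change score, Mann-Whitney on each, ANCOVA and rank ANCOVA. The plan does not say whether post or change scores are tested, so including both is a further assumption. The rate is the share of simulated null trials in which the reported p is below .05.

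| How the reported test is chosen | 0.5 | 0.7 | 0.8 |
|---|---|---|---|
| t-test, switched to Mann-Whitney on a Shapiro check | 5.9% | 5.6% | 5.0% |
| Smallest p of post t-test, change t-test, ANCOVA | 10.1% | 10.5% | 9.8% |
| Smallest p of all six | 12.0% | 12.8% | 12.4% |

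The first row uses 4,000 null trials per setting, the others 6,000. Each of the six tests alone rejects in 4.7-5.4%. The Monte Carlo standard error is √(0.05 × 0.95 / 4,000) = 0.3 points for the first row and √(0.125 × 0.875 / 6,000) = 0.4 points for the last. Repeat runs gave 5.1-5.6% for the first row and 11.8-13.1% for the last. Choice among the five outcomes is not included.

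**The case against.** A reader might infer that outcomes and tests were chosen with the results in hand, and so cannot count as pre-specified. The documents do not support that. They show how the section was written up, not when each decision was made, and a results-style rewrite of an earlier plan would look the same. This stands, and it limits the point to what the document demonstrates.

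Nor do the missing GG scores prove a late addition. Table 2 schedules other secondary information with a pointer to a later description, and no such description appears in the supplied text. The same is true of the steering committee. Prospective text may therefore be missing. BBS, ABC and 10MWT were scheduled in advance, so for these only the primary label is new. The recruitment paragraph also refers to statistical guidelines set in advance, although it does not give them. These objections stand too, but none of this text supplies a primary outcome or a decisive test.

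Finally, the plan ties the switch to non-parametric methods to assumption violations, not to p-values. On that reading the error rate is close to nominal, so it cannot be said that the rate must exceed 5%. The 12-13% figure is a ceiling for a selection process that the text does not describe.

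**Conclusion.** The point holds as a statement about this document. It does not demonstrate that the five primary outcomes, or the choice among t-test, Mann-Whitney, ANCOVA and rank ANCOVA, were pre-specified. It therefore does not support treating each .05 test as confirmatory. It is not evidence of selective reporting, and an earlier dated plan cannot be excluded.

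The size for one null outcome ranges from about 5-6% under the assumption-driven switch, through about 10% for the best of three tests, to a ceiling of about 12-13% for the best of six. The range rests on the assumed normality, the assumed correlations of 0.5 to 0.8 and the availability of both post and change scores. If one test was in fact fixed beforehand, the rate is 5%.

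**What to change.** State when the Data Analysis section was finalised relative to the 25% and 50% interim data and the final data. Then:

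1. **A dated plan from before access to outcome data exists.** Replace the section with it and list every departure.
2. **A dated pre-data record, such as the power calculation, documents only the outcome behind d = 0.39.** Treat as confirmatory only the between-group comparison of that outcome, with one named test at two-sided .05. Use the test in that record. If none is recorded, use the two-sample t-test on the scale from which d was calculated, which is the natural reading of a Cohen's d power calculation. Show the other listed tests for that outcome as sensitivity analyses only. Displaying them all without saying which one decides would leave the selection problem in place.
3. **No pre-data record identifies the outcome.** Label all results exploratory. Naming the outcome now would repeat the problem.

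Under 2 and 3, label the remaining outcomes and the session-count and site comparisons as post hoc or exploratory, with estimates and 95% intervals and no significance claim. Under 1, do the same for any of these that the dated plan does not cover.

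The cost is wording in this section and the report, plus a few table rows. The downside is that fewer results, possibly none, can be claimed as confirmatory.
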